**11. Fatal bleeding 5**

- A dichotomous endpoint of fatal bleeding defined as death attributable to bleeding according to the site investigator reporting or as judged via central adjudication.
- The endpoint is counted only for bleeding events occurring within 15 days to correspond to the intervention duration. Death from that bleeding event occurring after 15 days is included here.

**12. Heparin-induced thrombocytopenia (HIT)**

- A dichotomous endpoint of laboratory-confirmed HIT.

- The endpoint is censored at 15 days to correspond to the intervention duration.

**13. Deep venous thrombosis**

- A dichotomous endpoint of clinically detected deep venous thrombosis diagnosed at any time during the index hospitalization.

**14. Pulmonary embolism**

- A dichotomous endpoint of clinically detected pulmonary embolism diagnosed at any time during the index hospitalization.

**15. Ischemic cerebrovascular event**

- A dichotomous endpoint of ischemic cerebrovascular event (stroke).
- Assessed during the index hospitalization, up to 28 days

**16. Acute myocardial infarction**

- A dichotomous endpoint of acute myocardial infarction defined according to the universal definition of myocardial infarction.
- Assessed during the index hospitalization, up to 28 days

**17. Systemic arterial thromboembolism**

- A dichotomous endpoint of clinically diagnosed systemic arterial thrombosis or embolism
- Assessed during the index hospitalization, up to 28 days

**18. Major thrombotic event or death**

- A composite dichotomous endpoint of pulmonary embolism, ischemic cerebrovascular event, myocardial infarction, or systemic arterial thromboembolism diagnosed at any time during the index hospitalization or death in hospital

**19. All thrombotic events or death**

- A composite dichotomous endpoint of deep vein thrombosis, pulmonary embolism, ischemic cerebrovascular event, myocardial infarction, or systemic arterial thromboembolism diagnosed at any time during the index hospitalization or death in hospital

**20. Intracranial hemorrhage**

- A dichotomous endpoint of ischemic cerebrovascular event (stroke).
- Assessed during the index hospitalization, up to 28 days

**21. Hospital re-admission**

- A dichotomous endpoint of readmission to hospital within 90 days from randomization
- This endpoint will be reported descriptively using proportions, including for diagnoses of interest: bleeding, thrombotic event, MI, stroke, ventilatory support

**22. Renal replacement therapy**

- A dichotomous endpoint of initiation of renal replacement therapy during the index hospitalization among patients not on renal replacement therapy at baseline.
- Censored at day 90

**23. Acute kidney injury**

- A dichotomous endpoint of acute kidney injury (as defined by KDIGO) or requirement of renal replacement therapy during the index hospitalization among patients not on renal replacement therapy at baseline.
- Censored at day 90

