5.1 Inclusion Criteria

In order to be eligible to participate in this study, an individual must meet all of the following criteria:

- ≥ 18 years of age
- Hospitalized for COVID-19*
- Enrolled within 72 hours of hospital admittance or 72 hours of positive COVID test
- Expected to require hospitalization for > 72 hours
- See arm-specific Appendices for additional criteria and details

*It is strongly recommended to confirm SARS-CoV2 with a positive PCR or other commercial or public health assay prior to randomization. At centers where there is a delay in confirming the diagnosis, a sufficiently high clinical suspicion is sufficient to proceed with randomization as long as confirmation is expected within 24 hours.

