Pulmonary embolism will be confirmed by chest CT with PE protocol, pulmonary angiography or ventilation-perfusion scan. Events may also be defined without this imaging by the care team, as evidenced by, for example, "clot in transit" on echocardiogram. If PE is diagnosed and treated without imaging due to imaging availability concerns or risk of exposure to SARS CoV-2, this will be classified as probable PE. Later imaging is preferable in these cases when possible.

Stroke/ Peripheral Arterial Systemic Thromboembolism

Stroke or systemic embolism as diagnosed by imaging (i.e., head CT, lower extremity CT angiogram) or deemed "highly-likely" by the provider based on physical examination (i.e., acute hemiplegia thought to be due to stroke, acute distal lower extremity hypoperfusion). Systemic thromboembolism may involve the retinal artery, spinal cord or other vascular beds. Classification of ischemic vs. other etiologies is based on neuroimaging. Venous sinus thrombosis will be included in the category of vascular occlusion/ischemic stroke on the venous side. Primary CNS hemorrhage: intracerebral hemorrhage, subarachnoid hemorrhage, subdural hematoma, and rarely epidural hematoma or spinal hematoma. Secondary hemorrhagic stroke: blood associated with an ischemic infarct.

ICU Level of care disease state (severe illness)

Defined as receipt of cardiovascular or respiratory organ support as defined in the 21-day organ support free days. ICU level of care is defined as being on invasive or non-invasive mechanical ventilation, high flow nasal oxygen, or vasopressor therapy or ECMO support.

Myocardial infarction

Myocardial infarction is defined according to the universal definition of MI, which excludes myocardial injury e.g., isolated elevation of cardiac troponin. MI must include rise and fall of cardiac troponin above the 99th percentile with at least one of the following: symptoms of acute ischemia, ECG changes consistent with ischemia, new/presumed new wall-motion abnormalities or other imaging evidence of MI, abnormal coronary angiography (e.g. identification of a coronary thrombus).

Acute Kidney Injury

Acute kidney injury after enrollment is defined by KDIGO criteria for Acute Kidney Injury in the setting of not meeting these criteria upon enrollment:

Modified Stages:

- Stage 2: Serum Cr 2.0–2.9 times baseline
- Stage 3: Serum Cr \geq 3.0 times baseline, OR Increase in serum creatinine to \geq 4.0mg/dl, OR Initiation of renal replacement therapy

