#### 12.3. Analytic Approach for Secondary Dichotomous Endpoints

A Bayesian logistic regression model will be used for each dichotomous outcome. The model will always specify the “event” as the negative outcome and be parameterized so that an OR >1 implies benefit to patients. The model is the standard logistic link function model:

$$\log \left( \frac{\pi}{1 - \pi} \right) = \alpha - [factors]$$

References will be made to the factors in the model and their prior distribution. Many of these factors will be the same as the primary analysis model, with the same priors, as the parameters have similar interpretation. For example, all in-hospital mortality models should use the Beta prior distribution implied by the Dirichlet prior in the OSFD model. If not otherwise specified, the prior distribution for the main effect is  $\alpha \sim N(0, 1.82^2)$  (similar to a uniform prior on the probability scale).

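### SAP endpoint 23 omits the protocol's stage threshold and new-onset restriction for acute kidney injury, so injury present at randomization can be counted

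*SAP*

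**What the plan says.** Acute kidney injury is a secondary endpoint in Protocol 4.2.2. Protocol Appendix 2 (A2.2) defines it: "Acute kidney injury after enrollment is defined by KDIGO criteria for Acute Kidney Injury in the setting of not meeting these criteria upon enrollment". Under its modified stages, the lowest listed is "Stage 2: Serum Cr 2.0–2.9 times baseline". Stage 3 covers a creatinine ratio of 3.0 or more, or a rise to at least 4.0 mg/dl, "OR Initiation of renal replacement therapy".

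SAP Section 7, endpoint 23, is a dichotomous endpoint of "acute kidney injury (as defined by KDIGO) or requirement of renal replacement therapy", assessed "during the index hospitalization among patients not on renal replacement therapy at baseline" and "Censored at day 90". It gives no stage, does not require onset after enrollment, and does not point to Appendix 2. The SAP refers to a data dictionary for organ support-free days (Section 4.3 and endpoint 1), but not for kidney injury.

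On analysis, SAP 12.3 states: "A Bayesian logistic regression model will be used for each dichotomous outcome". SAP 12.7 sets the scale so that an odds ratio above 1 means benefit.

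**The concern.** The two documents define the same named endpoint differently in two respects: severity (stages 2 and 3, against no stated stage) and onset (new injury only, against injury during the stay in anyone not on RRT at baseline).

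The onset difference matters more for the estimate. Patients may be "Enrolled within 72 hours of hospital admittance or 72 hours of positive COVID test", so randomization can come days into the stay. Injury can then precede randomization and still fall within the index hospitalization. The severe cohort is on organ support at randomization, and the Arm C exclusions in A7.2.2 contain no renal criterion. If such a patient is counted because of the injury already present, treatment could not have prevented that event. Cases of this kind fall equally, on average, in both arms and attenuate any real benefit or harm.

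There is also a practical risk. Protocol A2.1 tells sites to assess outcomes by the Appendix 2 definitions, while Protocol Appendix 1 sends the reader to the SAP for the current analysis plan. Collection and analysis could follow different definitions.

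**Working it through.** The documents give no event rate, effect size, sample size or power for kidney injury, so there is no planned figure to reproduce. The check has a textual part and an illustrative part.

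**1. The definitions side by side**

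| Element | Protocol A2.2 | SAP endpoint 23 |
|---|---|---|
| Severity | Modified KDIGO stages 2 and 3 | KDIGO, no stage stated |
| Onset | After enrollment | Not stated; during the index hospitalization |
| Patients at risk | Not meeting the criteria at enrollment | Not on RRT at baseline |
| RRT | Initiation, as part of stage 3 | Requirement of RRT |
| Reference creatinine | Ratios to a baseline that is not defined | Not stated |

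The SAP states an at-risk restriction elsewhere when it wants one. Endpoint 22 counts initiation of RRT among those not already on it, and endpoint 35 is limited to patients without the symptom before COVID-19. Endpoint 23 makes the restriction for RRT only.

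**2. When existing injury would be counted**

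- If the reference is a value from before the injury, a patient who already meets a ratio criterion meets it again at the first in-hospital creatinine. This holds even if the window starts at randomization, provided the injury persists.
- If the reference is the enrollment value, the ratio at enrollment is 1 by construction, and the patient needs a further rise to meet a ratio criterion. On that reading, however, the protocol's own test of not meeting the criteria at enrollment does no work for the ratio criteria. This suggests, but does not establish, that Appendix 2 has an earlier value in mind.

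**3. Size of the attenuation**

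Let f be the share of each arm whose existing injury is counted as an event, and p the incident risk in the rest. The arm rate is f + (1 − f)p, and the risk difference shrinks by the factor (1 − f). Assumed, not from the documents: p = 15% control and 10% treated; f = 0 to 30%.

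| f | Control | Treated | Event OR | Benefit-scale OR (1/event OR) | Risk difference |
|---|---|---|---|---|---|
| 0 | 15.0% | 10.0% | 0.63 | 1.59 | 5.0 points |
| 10% | 23.5% | 19.0% | 0.76 | 1.31 | 4.5 points |
| 20% | 32.0% | 28.0% | 0.83 | 1.21 | 4.0 points |
| 30% | 40.5% | 37.0% | 0.86 | 1.16 | 3.5 points |

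For f = 20%: control 0.2 + 0.8 × 0.15 = 0.32; treated 0.2 + 0.8 × 0.10 = 0.28; event OR = (0.28/0.72)/(0.32/0.68) = 0.83. Swapping the arms gives the same attenuation of a harm.

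**4. Whether exclusion costs more than it saves**

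A second assumed case uses a frequentist two-proportion calculation (two-sided 0.05, 1:1) as a proxy for the Bayesian logistic model. Incident risk is 20% versus 14.3%, a benefit OR of 1.50. With no existing injury, 682 per arm gives 80% power. If 20% have existing injury and are counted, the rates become 36% versus 31.4%, the OR falls to 1.23, and power at 682 per arm is 43%. If they are excluded, 0.8 × 682, about 545 per arm, remain and power is 71%. In this case exclusion loses less than counting them does.

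**The case against.** The strongest reply is that endpoint 23 may be shorthand. Appendix 2 also opens by naming KDIGO before listing its modified stages, so the SAP's phrase could mean the same thing. The SAP nowhere says any stage, and it does not say that findings before randomization count. This stands as a caution about intent. It does not remove the mismatch: the protocol calls its stages modified, the SAP does not cite them, and a programmer working from the SAP alone has no basis for applying them.

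A reader might go further and infer that every patient with kidney injury at randomization becomes an event whatever the treatment does. The documents do not support that, because the outcome depends on the undefined reference creatinine. With the enrollment value as reference, f in the table would be near zero for the ratio criteria.

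A reader might also infer that admitting milder injury dilutes the effect. That does not follow either. Adding the same number of mild cases to both arms would show attenuation only because it assumes that treatment has no effect on mild injury. If treatment also reduces mild injury, the broader endpoint gains informative events. What can be said is that it is a different outcome.

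Finally, the impact is limited. Kidney injury is one of 35 SAP endpoints and is not among the primary, key secondary or key safety endpoints in SAP 3.1. The superiority and futility rules in SAP 4.4 and 12.13 do not use it. The randomized comparison remains valid under either definition. All of this stands.

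The SAP is a draft of 30 March 2021 and the protocol is version 1.2 of 19 October 2021. The dates may explain the difference, but both are the texts supplied and they should agree.

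**Conclusion.** The mismatch is certain from the text: endpoint 23 lacks both the stage threshold and the new-onset restriction of Protocol A2.2. That injury present at randomization can be counted is a consequence of the wording; that it will be counted is not established, because neither document defines the reference creatinine.

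Where such cases are counted, the direction is clear: any true effect moves toward no difference. If there is no true effect, no spurious one is created. The size cannot be derived from the documents. The fall in the benefit odds ratio from 1.59 to between 1.31 and 1.16 rests wholly on assumed incident risks and on 10% to 30% of each arm having existing injury that is counted.

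The matter should be corrected before analysis. It affects the precision and interpretation of one non-key secondary result, and no stopping trigger or primary conclusion.

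**What to change.** In SAP endpoint 23:

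- Cite Protocol A2.2 and restate it: new modified KDIGO stage 2 or 3 injury, or initiation of RRT, after randomization, among patients who neither meet the criteria nor receive RRT at enrollment.
- State the reference creatinine for the ratio criteria and for classifying injury at enrollment, and the rule when no earlier value exists. Copying A2.2 without this leaves the split between existing and new injury undetermined.
- Report any-stage injury as a sensitivity analysis.

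If the broader definition is intended, amend the protocol to match and keep the incident stage 2 or 3 version as the sensitivity analysis.

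The main change is wording. The A7.6 schedule already has a chemistry panel at screening/enrollment and in hospital. There are two costs: a smaller denominator, and some uncertainty in classifying injury at enrollment, because the schedule lists no creatinine from before enrollment.

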**24. The World Health Organization (WHO) 8-point ordinal scale, value on day 14.**

- A modified WHO ordinal scale will be used:
  - 0 + 1 + 2 = No longer hospitalized
  - 3 = Hospitalized, no oxygen therapy
  - 4 = Oxygen by mask or nasal prongs
  - 5 = Non-invasive ventilation or high-flow oxygen
  - 6 = Intubation and mechanical ventilation
  - 7 = Ventilation + additional organ support: vasopressors, renal replacement therapy (RRT), ECMO
  - 8 = Death

**25. 28-Day Outcome of Ventilator or Death**

- Binary variable to indicate whether the patient is on a ventilator on Day 28 or deceased by day 28.
- Those discharged before day 28 who are not on a ventilator will be considered to not be on a ventilator at day 28.

**26. Ventilator Support**

- Dichotomous indicator of requiring all ventilator support (invasive and non-invasive) or death over the index hospital stay
- Truncated at 90 days

**27. Any organ support**

- Dichotomous indicator of requiring any organ support or death over the index hospital stay
- Truncated at 90 days

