4.2.2 Secondary Endpoints

- Categorization of the primary endpoint into a three-level ordinal outcome (Death, invasive mechanical ventilation without death, neither invasive mechanical ventilation nor death)
- Categorization of the primary endpoint into a three-level ordinal outcome (Death, organ support (any respiratory or cardiovascular) without death, neither organ support nor death) (for moderate illness severity at enrollment)
- Days free of death and respiratory and cardiovascular organ support and renal replacement therapy (RRT) during Index Hospitalization through Day 28. If the patient dies at any time during the index hospital stay through 90 days, they are assigned the worst possible score of -1.
- A composite endpoint of death, pulmonary embolism, systemic arterial thromboembolism, myocardial infarction, or ischemic stroke during hospitalization or at 28 days after enrollment (whichever is earlier) – “major thrombotic events or death”
- 28 Day Hospital free days (non-ICU level patients)
- 28 Day Ventilator-Free Days (ICU level patients)
- 28 Day Vasopressor-Free Days (ICU level patients)
- 28 Day Renal Replacement Free Days
- Hospital readmission within 28 days
- Acute kidney injury
- Deep vein thrombosis
- Pulmonary embolism
- Systemic arterial thrombosis or embolism
- Myocardial infarction
- Ischemic stroke
- Renal replacement therapy
- Use of extracorporeal membrane oxygenation (ECMO) support
- Mechanical circuit (dialysis or ECMO) thrombosis
- WHO ordinal scale (peak scale over 28 days, scale at 14 days, and proportion with improvement by at least 2 categories compared to enrollment, at 28 days)
- All-cause mortality at 28 days
- All-cause mortality during initial hospitalization (includes death after 28 days)
- All-cause mortality at 90 days

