Autopsy and clinical data highlight the potential role of platelets and their precursors in the pathogenesis of COVID-19.¹⁻³ Platelets are shed into circulation by megakaryocytes, and during this process, megakaryocytes distribute their transcriptome into platelets. Once in the circulation, platelets can respond to local and systemic conditions and induce monocyte, macrophage and endothelial cell activation.⁴⁻⁶ Prior to COVID-19, it was described that platelet-viral interactions alter the platelet transcriptome and induce a proinflammatory immune mediated platelet phenotype.⁷ Consistently, platelets isolated from COVID-19 patients are hyperreactive and have an altered transcriptomic signature compared to disease-free controls.³ Biomarkers of platelet activity are elevated in COVID-19 and are associated with thrombosis and all-cause mortality even after multivariable adjustment. These data suggest that platelets are activated in COVID-19 and represent a therapeutic target for improved clinical outcomes.

A7.2. Eligibility Criteria for Arm C

Note that to be eligible for randomization in a specific comparison during this adaptive trial patients are required to meet eligibility criteria for at least the standard of care arm and one comparator arm.

A7.2.1 Inclusion Criteria for Arm C

Same as the Master Protocol.

A7.2.2 Exclusion Criteria for Arm C

In addition to the exclusion criteria noted in the master protocol, arm-specific exclusion criteria are as follows:

- Moderate illness severity – non-ICU level of care at the time of randomization (not receiving HFNO, NIV, IV, vasopressors or inotropes, or ECMO)
- Contraindication to P2Y12 inhibitor, including but not limited to
 - known bleeding within the last 30 days requiring emergency room presentation or hospitalization
 - known hypersensitivity to all P2Y12 inhibitors
 - known history of an inherited or active acquired bleeding disorder
 - history of intracranial hemorrhage at any time
- Platelet count < 50 x 10⁹/L
- Hemoglobin < 8 g/dL
- Requirement for ASA > 162mg per day that it cannot be stopped safely
- Requirement for P2Y12 inhibitor that cannot be stopped safely

A7.3 Study Agents

Arm C consists of the combination of standard of care treatment, plus an antiplatelet agent in the P2Y12 inhibitor family.

A7.3.1. Standard of Care Treatment

Please refer to the manual of operations for recommended standard of care treatment.

A7.3.2. P2Y12 Inhibitor

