#### 4.1. Patient Cohorts

There are two *illness states* defined for this analysis; the severe and moderate illness cohorts. The *severe illness state* is defined as a hospitalized patient on ICU-level organ-support at time of randomization. The *moderate illness state cohort* is defined as a hospitalized patient that is not in the severe illness state.

The primary analysis for the study creates two distinct populations to analyze potential differential benefit of the interventions. In this study these distinct groups are labeled as *cohorts*. The two cohorts are: 1) patients in the severe illness state; 2) patients in the moderate illness state at randomization.

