**29. Categorization of the primary endpoint - organ support free days**

- Three-level outcome: No organ support without death, some organ support without death, death

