**30. Four-level organ support**

- Four-level outcome: No organ support without death, some organ support without invasive mechanical ventilation and without death, some invasive mechanical ventilation without death, death

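### SAP endpoint 27 (any organ support or death) is an event for essentially every severe-cohort patient in both arms, yet nothing stops it being modelled there; endpoint 29 separately loses the protocol's moderate-only limit

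*SAP*

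**What the plan says.** **Cohorts.** SAP 4.1 says the severe illness state "is defined as a hospitalized patient on ICU-level organ-support at time of randomization". Protocol Appendix 2 uses the same components for ICU level of care: "Defined as receipt of cardiovascular or respiratory organ support as defined in the 21-day organ support free days".

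**Endpoint 27 (SAP Section 7).** "Dichotomous indicator of requiring any organ support or death over the index hospital stay", truncated at 90 days. No cohort is named, and there is no requirement that the support be new.

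**Endpoint 29.** "Three-level outcome: No organ support without death, some organ support without death, death". Protocol 4.2.2 lists the same three levels but closes the entry with a restriction: "for moderate illness severity at enrollment". The SAP entry has no such restriction.

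**Endpoint 30.** This has four levels. It splits organ support by invasive ventilation, with one level being "some organ support without invasive mechanical ventilation and without death". No cohort is named.

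**Baseline limits elsewhere.** The SAP restricts endpoints 7, 22 and 23 (renal replacement-free days, renal replacement therapy, acute kidney injury) to patients not on renal replacement therapy at baseline.

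**Modelling rules.** Section 7 says the listed endpoints will be analyzed. Section 12.3 gives each dichotomous endpoint a Bayesian logistic model, with default intercept prior N(0, 1.82²). Section 12 exempts only events of low frequency. Section 12.1 item 13 gives a standard normal treatment prior for a single-cohort analysis. Section 12.5 gives a normal prior with SD 10 for cohort analyses, without borrowing. Section 12.6 lets the statisticians alter an unstable model and note the change.

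**The concern.** An endpoint that a patient already meets on entering the trial cannot respond to treatment. For severe patients endpoint 27 is met at randomization, so the arms cannot differ on it except through the few patients whom a definitional mismatch might leave as non-events. The exemption for rare events does not cover an event at or near 100%. Followed literally, the SAP would publish an odds ratio, a credible interval and a probability of superiority for the severe cohort that say nothing about P2Y12 inhibition. A reader of the table could not tell that from a real estimate.

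Endpoint 29 has a different and smaller problem. The protocol recognised that its lowest-risk level is meaningful only for moderate patients, and the SAP does not carry that over.

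**Working it through.** The documents give no event rate, sample size or power for these endpoints, so there is no planned figure to reproduce.

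**Step 1: event rate.** Severe means on organ support at randomization, and endpoint 27 counts any organ support or death during the stay. Under the SAP's definitions the rate is therefore n/n in each arm, with a risk difference of 0.

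**Step 2: model.** Under SAP 12.3, logit(p) = α for control and α − θ for P2Y12, with OR = exp(θ) and OR > 1 meaning benefit. When all n patients per arm are events, the likelihood is

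[1/(1+exp(−α))]ⁿ × [1/(1+exp(−(α−θ)))]ⁿ.

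It rises without limit in α and falls in θ, so it has no maximum. The priors alone keep the posterior in place.

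**Step 3: why the posterior is not simply the treatment prior.** The upper 97.5% point of the intercept prior is 1.96 × 1.82 = 3.57, a control event probability of 1/(1+exp(−3.57)) = 0.973. A 100% rate lies in the tail of that prior. The model can still raise the fitted P2Y12 event probability by making θ negative, which it reads as harm.

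**Step 4: posterior on a grid.** Inputs are α ~ N(0, 1.82²) from SAP 12.3 and θ ~ N(0,1) from 12.1 item 13 or N(0, 10²) from 12.5. Covariates are omitted. The n per arm is an assumption, shown over a range.

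| n per arm | θ SD 1: median OR | θ SD 1: Pr(OR>1) | θ SD 10: Pr(OR>1) | θ SD 10: upper 95% bound for OR |
|---|---|---|---|---|
| 50 | 0.59 | 0.27 | 0.03 | about 1.3 |
| 100 | 0.57 | 0.25 | 0.03 | about 1.1 |
| 250 | 0.53 | 0.22 | 0.02 | about 0.9 |
| 500 | 0.51 | 0.21 | 0.02 | about 0.8 |

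Before any data Pr(OR>1) is 0.50. The N(0,1) prior interval for the OR is exp(±1.96) = 0.14 to 7.1; at 250 per arm the posterior interval is 0.10 to 2.7. With SD 10 the interval excludes 1 on the harm side at 250 or more per arm, although the arms are identical.

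**Step 5: sensitivity.**
- *Wider intercept prior, SD 10.* Pr(OR>1) is 0.48 to 0.47 with θ SD 1, and 0.30 to 0.28 with θ SD 10.
- *Near-flat intercept prior, SD 100.* Pr(OR>1) is 0.497 and 0.482. Only here does the posterior roughly return to the treatment prior.
- *One non-event per arm (249/250 each).* With θ SD 1, the log-OR has SD 0.75 and Pr(OR>1) is 0.28, so the prior still dominates. With θ SD 10, Pr(OR>1) is 0.17 and the upper bound rises to 3.0, so the interval no longer excludes 1.
- *Borrowing.* The documents give no hyperpriors. I assumed moderate events of 75/250 on control and 62/250 on P2Y12, overall treatment mean N(0,1), between-cohort SD 0.15 to 1, and severe-cohort effect prior SD 1 or 10. The severe Pr(OR>1) then runs from 0.03 to 0.81, set only by those two assumed SDs.

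**Step 6: endpoints 29 and 30 in severe patients.** For endpoint 29 the no-support level is empty, leaving survival with support against death. Death here is the −1 of the primary endpoint, which is how endpoint 2 is defined. With an assumed 75/250 deaths in each arm, the OR is about 1.0 (95% interval 0.69 to 1.46) and the log-OR SD is 0.19 against a prior SD of 1. That is informative, but it duplicates endpoint 2. Endpoint 30 keeps three of its four levels: support without invasive ventilation, invasive ventilation, and death.

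**The case against.** **The protocol limit belongs to endpoint 29.** A reader might infer that the SAP removed a protocol restriction from endpoint 27. It did not: the restriction is attached to the three-level endpoint. Endpoint 27 is the two-level collapse of that endpoint and has no entry of its own in protocol 4.2.2. The case against modelling 27 in severe patients rests on the cohort definition.

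**Endpoints 29 and 30 are not empty of information.** A reader might group all three together. Step 6 shows otherwise. SAP 12.1 item 12 already merges an unobserved ordinal level with the next worse one. It is written for the primary outcome but extends naturally to endpoint 30.

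**Borrowing may not apply.** A reader might infer that the severe effect would be copied from the moderate cohort. Borrowing is described for the primary analysis, SAP 12.5 rules it out for cohort analyses, and 12.3 says only that many factors match the primary model. It is a possibility, not a stated rule.

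**The rate may be slightly below 100%.** SAP 4.3 counts high-flow oxygen as organ support only at FiO2 of 0.4 or more, while protocol Appendix 2 asks only for a titratable FiO2. A few patients enrolled as severe could be non-events. This stands, and it softens the SD 10 result, but the estimate stays prior-dominated. The data dictionary cited by the SAP was not available and may hold a restriction.

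**The SAP covers both cohorts.** It is a March 2021 draft. The October 2021 protocol retired the moderate P2Y12 arm (Appendix 8) and left Arm C, which excludes moderate patients (A7.2.2). That is a matter of document timing, and endpoint 27 is informative in the moderate cohort that the SAP covers.

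**The practical effect is limited.** Endpoint 27 is not among the expedited-report endpoints in SAP 3.1 and drives no trigger in 4.4 or 12.13. Section 12.6 would let a statistician intervene. All of this stands and lowers the priority. But 12.6 names no endpoint, and a proper-prior model can run without visible failure, so the clause may never be invoked.

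**Conclusion.** The concern holds for endpoint 27 in the severe cohort. By the SAP's own definitions essentially every severe patient is an event in both arms, and the SAP as written would model it. The result would lean towards harm for identical arms, with Pr(OR>1) about 0.27 to 0.21 under a N(0,1) treatment prior and about 0.03 to 0.02 under SD 10. These figures assume 50 to 500 per arm, the stated intercept prior and no covariates. Their size depends on covariates and priors that the SAP does not fully specify.

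A reader might go further and expect a false declaration of harm or futility. The documents do not support that: the SAP 4.4 triggers apply to organ support-free days only. Even in the most extreme case in the table, Pr(OR<1) is about 0.98, short of the 99% in SAP 12.7.

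For endpoint 29 the omitted restriction is a real mismatch with protocol 4.2.2; its consequence in severe patients is duplication of endpoint 2. Endpoint 30 needs only a note. Overall this is a minor but genuine error in a secondary endpoint.

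**What to change.** 1. Limit endpoint 27 to the moderate cohort, or define it as new organ support or death among patients not on organ support at baseline, as the SAP already does for its renal replacement endpoints. State that it will not be modelled in severe patients.
2. Restore on endpoint 29 the restriction in protocol 4.2.2.
3. For severe patients rely on endpoint 31 (death, invasive ventilation, neither), which is already in the SAP and matches a protocol endpoint without a cohort limit, and on endpoint 30 with its empty level merged. Note that patients already on invasive ventilation at randomization contribute only survival or death to these two endpoints; the baseline ventilation factor in SAP 12.1 item 8 should be kept in those models.

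The cost is a few lines of SAP text and fewer severe-cohort models. No data collection changes.
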